Background and Rationale:	The primary “non-psychoactive” phytochemical in cannabis CBD, is thought to have a broad range of therapeutic properties, including amelioration of the adverse psychological effects of THC, like impaired cognition (Osborne, Solowij, & Weston-Green, 2017; Zuardi, 2008). Here, we aim at investigating the effect of CBD on episodic memory.
Objective(s):	Primary objective of the study: Influence of CBD on episodic memory functions in healthy subjects Secondary objectives: Influence on working memory
Outcome(s):	The primary endpoints will be performance in a verbal memory task ([name], Henke et al. 2003). The secondary endpoints will be performance in a working memory test.
Study design:	Placebo controlled, randomized, double blind, cross-over design.
Inclusion / Exclusion criteria:	
Inclusion criteria
 
 • Normotensive (BP between 90/60mmHg and 140/90mmHg) • BMI between 18 and 30 kg/m² • Male or female • Aged between 18 and 30 years • Native or fluent German-speaking 
Exclusion criteria
 
 • Acute or chronic psychiatric disorder including drug or alcohol abuse • Known hypersensitivity or allergy to propylene glycol • Women who are pregnant or breast feeding • Smoking (> 5 cigarettes per day) • Participation in one of our previous studies using the same verbal test in the past 2 years • Participation in a study with investigational drug within the 30 days preceding and during the present study • Intake of CBD / THC within the 7 days preceding and during the present study in any application form • Long-term systemic medication or topical steroids to treat an underlying disease within last 3 months

Measurements and procedures:	
 • Screening visit with questionnaires. • Visit 1, 2 (Visit 2 2 week + 8 week after visit 1): A urine sample will be taken to control for pre-visit cannabis consumption. Subject will learn a list of 15 words followed by an immediate recall. Then they will be randomized to vape (verum or placebo) for 15min. They will perform a working memory test (n-back) and rate different VAS (mood, arousal, motivation, tiredness, headache, tolerance). And then the episodic memory test words short delay will be performed. 
Assessment of safety: AE recording

Study Product / Intervention:	Single vape of 0.25ml 5% CBD e-liquid Citrus Fruits, Pharma Hemp (12.5mg CBD). We estimate 15min vape time.
Control Intervention (if applicable):	Single vape of 0.25ml e-liquid La Baronne Jaune, BORDO2 tastes like lemon and madeleine. 15min vape time.
Number of Participants with Rationale:	We are interested to detect cannabidiol effects with at least medium effect sizes. The estimation of N=34 is based on a power analysis using dependent t-tests assuming to detect a medium effect size ($d_z = 0.5$) with a power of 80% at $\alpha = 0.05$ (software: G-power 3).
Study Duration:	Study duration is estimated 6 months
Study Schedule:	First participant in 10/2018 (planned) Last participant out 03/2019 (planned)
Investigator(s):	
Sponsor-Investigator [name] [name], MD Division of Cognitive Neuroscience University of Basel [name] [contact] [contact] Email: [contact]
 
Subinvestigator [name] Division of Cognitive Neuroscience University of Basel [name] [contact] [contact] Email: [contact]

Study Centre(s):	Division of Cognitive Neuroscience University of Basel
Statistical Considerations:	A significance level of $p < 0.05$ (two-sided) will be considered as significant. All analyses will be done in R. The differences between the experimental conditions will be analyzed using linear mixed models in combination with analysis of variance (SS II).

GCP Statement:	This study will be conducted in compliance with the protocol, the current version of the Declaration of Helsinki, the ICH-GCP or ISO EN 14155 (as far as applicable) as well as all national legal and regulatory requirements.
-----------------------	---

ABBREVIATIONS

AE	Adverse Event
BASEC	Business Administration System for Ethical Committees, (https://submissions.swissethics.ch/en/)
BMI	Body mass index
BP	Blood pressure
CA	Competent Authority (e.g. Swissmedic)
CB1 receptors	Cannabinoid 1 receptors
CB2 receptors	Cannabinoid 2 receptors
CBD	Cannabidiol
CEC	Competent Ethics Committee
CRF	Case Report Form
ClinO	Ordinance on Clinical Trials in Human Research (in German: KlinV, in French: OClin, in Italian: OSRUm)
eCRF	Electronic Case Report Form
CTCAE	Common terminology criteria for adverse events
DSUR	Development safety update report
EKNZ	Ethikkommission Nordwestschweiz
GCP	Good Clinical Practice
IB	Investigator's Brochure
Ho	Null hypothesis
H1	Alternative hypothesis
HRA	Federal Act on Research involving Human Beings (in German: HFG, in French: LRH, in Italian: LRUm)
IMP	Investigational Medicinal Product
IIT	Investigator-initiated Trial
ISO	International Organisation for Standardisation
ITT	Intention to treat
MADRS-S	Montgomery-Asperg Depression Self-rating Scale
MD	Medical Device
MedDO	Medical Device Ordinance (in German: MepV, in French: ODim)
NA	Not applicable
NG/ML	Nanogram per millilitre
PI	Principal Investigator
SD	Source Data
SDV	Source Data Verification
SOP	Standard Operating Procedure
SPC	Summary of product characteristics
SUSAR	Suspected Unexpected Serious Adverse Reaction
THC	Delta-9-tetrahydrocannabinol
TMF	Trial Master File

STUDY SCHEDULE

Procedure	Visit	Duration (min)	Starting time Visit 1 1 day (+ 3 month) after Tel. Screening	Starting time Visit 2 2 week (+ 8 week) after Visit 1
Telephonescreening				
Inclusion / Exclusion criteria		10	-	-
Screening				
Informed consent	Visit 1	10	00:10	-
MADRS-S		5	00:20	-
Sociodemographic questionnaire		2	00:25	-
Mental - Health questionnaire		5	00:27	-
Concomitant medication		2	00:32	-
Inclusion / Exclusion criteria		1	00:34	-
Test battery 1, 2				
Urine sample	Visit 1, Visit 2 (cross-over)	8	00:35	00:00
AE / Medication Log		1	00:43	00:08
Primary Endpoint: Words learning and immediate recall		2	00:44	00:09
Vape		15	00:46	00:11
Secondary Endpoint: n-back		15	01:01	00:26
VAS of mood, arousal Confounding factors: VAS of motivation, tiredness, headache, tolerance		1	01:16	00:41
Primary Endpoint: Words short delay recall		3	01:17	00:42
Overall time			80min	45min
End Visit 1 and Visit 2				

1.4 Laboratory

Not applicable

1.6 Data Safety Monitoring Committee

A data safety monitoring will not be formed due to the fact that no extended or unexpected safety concerns are anticipated.

1.7 Any other relevant Committee, Person, Organisation, Institution

Not applicable

2. ETHICAL AND REGULATORY ASPECTS

The decision of the CEC authority concerning the conduct of the study will be made in writing to the Sponsor-Investigator before commencement of this study. The clinical study can only begin once approval from all required authorities has been received. Any additional requirements imposed by the authorities shall be implemented.

2.1 Study registration

The study will be registered on clinicaltrials.gov and kofam.ch.

2.2 Categorisation of study

This study is classified as other clinical trial with persons.

The use of CBD e-liquid classified as foodstuff and commodities (according to Swissmedics: <https://www.swissmedic.ch/swissmedic/de/home/news/mitteilungen/produkte-mit-cannabidiol--cbd---ueberblick.html>) in usual quantity and dose entails only minimal risks and burdens and justifies the risk categorization A. CBD e-liquids are available on the Swiss market. The experimental setting entails only minimal risks and burdens to the well-being of subjects.

2.3 Competent Ethics Committee (CEC)

The sponsor/investigator will obtain approval from CEC (EKNZ) before the start of the clinical trial.

The sponsor/investigator will report all changes in the research activity and all unanticipated problems involving risks to humans; including in case of planned or premature study end and the final report and no changes are made to the protocol without prior EKNZ approval, except where necessary to eliminate apparent immediate hazards to study participants.

Premature study end or interruption of the study is reported within 15 days. The regular end of the study is reported to the EKNZ within 90 days, the final study report shall be submitted within one year after study end. Amendments are reported according to chapter 2.10.

2.4 Competent Authorities (CA)

Not applicable

2.5 Ethical Conduct of the Study

The study will be carried out in accordance to the protocol and with principles enunciated in the current version of the Declaration of Helsinki, the guidelines of Good Clinical Practice (GCP) issued by ICH, in case of medical device: the European Regulation on medical devices 2017/745 and the ISO Norm 14155 and ISO 14971, the Swiss Law and Swiss regulatory authority's requirements. The CEC and regulatory authorities will receive annual safety and interim reports and be informed about study stop/end in agreement with local requirements.

2.6 Declaration of interest

The authors certify that they have no intellectual, financial or proprietary conflict and are independent.

2.7 Patient Information and Informed Consent

During the telephone screening the subinvestigator will explain to each participant the nature of the study, its purpose, the procedures involved, the expected duration, the potential risks and benefits and

any discomfort it may entail. Each participant will be informed that the participation in the study is voluntary and that he/she may withdraw from the study at any time.

The participant must be informed that his/her medical records may be examined by authorised individuals other than their treating physician.

All participants for the study will be provided a participant information sheet and a consent form describing the study and providing sufficient information for participant to make an informed decision about their participation in the study. The information will be sent by e-mail to interested voluntary participants after telephone screening. Details see chapter 9.3. The interested voluntary will be given time between telephone screening and screening (at least one day) for his/her decision to participate.

The participant information sheet and the consent form will be submitted to the CEC to be reviewed and approved. The formal consent of a participant, using the approved consent form, must be obtained before the participant is submitted to any study procedure.

The participant should read and consider the statement before signing and dating the informed consent form, and should be given a copy of the signed document. The consent form must also be signed and dated by the investigator (or his designee) at the same time as the participant sign, and it will be retained as part of the study records.

2.8 Participant privacy and confidentiality

The investigator affirms and upholds the principle of the participant's right to privacy and that they shall comply with applicable privacy laws. Especially, anonymity of the participants shall be guaranteed when presenting the data at scientific meetings or publishing them in scientific journals.

Individual subject medical information obtained as a result of this study is considered confidential and disclosure to third parties is prohibited. Subject confidentiality will be further ensured by utilising subject identification code numbers to correspond to treatment data in the computer files.

For data verification purposes, authorised representatives of the Sponsor-Investigator or an ethics committee may require direct access to parts of the medical records relevant to the study, including participants' medical history.

2.9 Early termination of the study

The Sponsor-Investigator may terminate the study prematurely according to certain circumstances, for example:

- Insufficient participant recruitment

2.10 Protocol amendments

Substantial amendments are only implemented after approval of the CEC.

Under emergency circumstances, deviations from the protocol to protect the rights, safety and well-being of human subjects may proceed without prior approval of the sponsor and the CEC. Such deviations shall be documented and reported to the sponsor and the CEC as soon as possible.

All non-substantial amendments are communicated to the CEC within the Annual Safety Report (ASR).

3. BACKGROUND AND RATIONALE

3.1 Background and Rationale

Cannabis is thought to be the most commonly used illicit substance (Hall & Degenhardt, 2007). Delta-9-tetrahydrocannabinol (THC) and cannabidiol (CBD) are the two major constituents of cannabis. THC is psychoactive and binds to cannabinoid 1 (CB1) receptors located in brain and the periphery, as well as to cannabinoid 2 (CB2) receptors which are located exclusively on nonneural tissue, such as immune cells (Pertwee, 1997) or glial cells (Nunez et al., 2004). In contrast, CBD has little affinity to CB1 and CB2 receptors (Bisogno et al., 2001; Showalter, Compton, Martin, & Abood, 1996) and is not psychoactive.

Prolonged frequent use of THC, has been associated with deleterious effects on psychological functions, including increased risk of developing schizophrenia-related psychotic episodes (Di Forti et al., 2015; Moore et al., 2007), impaired cognition (Broyd, van Hell, Beale, Yucel, & Solowij, 2016; Solowij & Michie, 2007), and alteration in brain structure (Lorenzetti, Solowij, & Yucel, 2016) and function (Bhattacharyya, Crippa, Martin-Santos, Winton-Brown, & Fusar-Poli, 2009; Martin-Santos et al., 2012). Furthermore, acute exposure to high doses of THC can also produce psychotic episodes in healthy individuals that largely resemble positive symptoms of schizophrenia (Henquet, Di Forti, Morrison, Kuepper, & Murray, 2008).

In contrast, the primary “non-intoxicating” phytochemical in cannabis, CBD, is thought to have a broad range of therapeutic properties, including amelioration of the adverse psychological effects of THC. Moreover, CBD shows pro-cognitive effects and has, in multiple studies, been shown to protect against the detrimental cognitive effects of THC (Osborne et al., 2017; Zuardi, 2008). Regarding the effect of CBD on episodic memory, naturalistic human studies found that THC was associated with impaired learning and memory, but that the amount of CBD within cannabis was correlated with less impaired cognition (Morgan et al., 2012; Morgan, Schafer, Freeman, & Curran, 2010). A placebo-controlled between-subject study using participants with the diagnosis of schizotypy found reduced performance in an emotional recognition task in the THC groups as compared to a THC plus CBD group. Interestingly, CBD administration significantly improved accuracy in the emotional recognition task beyond placebo levels (Hindocha et al., 2015). However, an imaging study in healthy subjects found no effect of THC (10mg), CBD (600 mg) or placebo on cognitive task performance, but only on brain activations (Bhattacharyya et al., 2010).

Although the precise pharmacological mechanisms and neurocircuitry responsible for the deleterious vs. therapeutic properties are still being investigated, it is assumed that CBD indirectly influence CB1 receptors as CBD has low affinity for CB1 and CB2 receptors (McPartland, Duncan, Di Marzo, & Pertwee, 2015). Moreover, CBD interacts with the 5-HT_{1A} as an agonist (Russo, Burnett, Hall, & Parker, 2005). In general, neurotransmission through the brain’s endocannabinoid system has been shown to influence emotional memory processing through changes in dopamine signaling within the mesolimbic system (for a review see (Hudson, Rushlow, & Laviolette, 2018)). Here, we aim at investigating the effects of CBD on episodic memory.

3.2 Investigational Product (treatment, device) and Indication

Refer to chapter 8.1.

3.3 Preclinical Evidence

N/A

3.4 Clinical Evidence to Date

Only a few studies investigated the effect of CBD alone on episodic memory (see 3.1). In summary, animals and a few human studies showed that CBD has the potential to limit THC induced cognitive impairments. However, we are interested to investigate the effect of CBD on episodic memory in

humans.

3.5 Dose Rationale / Medical Device: Rationale for the intended purpose in study (pre-market MD)

The CBD doses used in describes studies in chapter 3.1 varies from 16 mg to 600 mg of CBD. Due to practical reasons and reasons of compliance, we have chosen a dose of 12.5 mg dose of CBD based on the estimated time taking to vape such a dose (15 minutes).

3.6 Explanation for choice of comparator (or placebo)

We will use a placebo vaping product (does not include CBD) tasting similar to intervention vaping product as a comparator.

3.7 Risks / Benefits

Benefits: current evidences suggests that CBD has the ability to reduce psychotic, anxiety and withdrawal symptoms (Mandolini et al., 2018) and amelioration of the adverse psychological effects of THC (Osborne et al., 2017).

Risks: sedative actions like somnolence and increase of sleep duration (for review see (Zuardi, 2008)). Therefore, subjects will not be allowed to drive home by a vehicle after study participation.

3.8 Justification of choice of study population

This study aims to gain knowledge about memory processes in healthy participants. We will include male and female subjects between 18 and 30 years.

4. STUDY OBJECTIVES

4.1 Overall Objective

The purpose of this study is to evaluate whether CBD has an influence on episodic memory functions in healthy participants.

4.2 Primary Objective

The study seeks primarily to determine the effect of CBD on episodic memory functions.

4.3 Secondary Objectives

The secondary objects are to assess the Influence of CBD on working memory.

4.4 Safety Objectives

The study aims to assess tolerability of CBD in terms of incidence of side effects e.g. headache, gastrointestinal side effects etc.

5. STUDY OUTCOMES

5.1 Primary Outcome

The primary endpoint will be the performance in a **verbal memory task** ([name], Henke et al. 2003), i.e. number of correctly recalled words (hits). Participants will view three series of five semantically unrelated nouns with the instruction to learn the words for immediate (after each series) and delayed (30 minutes after learning) free recall. Words are presented at a rate of 2 seconds.

5.2 Secondary Outcomes

Working memory will be assessed by means of a letter **0-back and 2-back task** (Papassotiropoulos et al., 2011). The 0-back condition serves as a low-load control condition, measuring general attention and does not require the manipulation of information within working memory. In the 2-back condition, participants have to compare the currently presented letter with the one presented 2 steps before and have to indicate whether they are identical or not. The 2-back condition requires online monitoring, updating and manipulation of remembered information and therefore is assumed to involve key processes of working memory (Owen, McMillan, Laird, & Bullmore, 2005). Accuracy and reaction time will be measured. The tasks lasts about 15 minutes.

5.3 Other Outcomes of Interest

Current mood and arousal will be assessed by means of 10 cm visual analog scales (VAS) with the two end points—“lowest level” (0) and “highest level” (10).

VAS of motivation, tiredness, headache and tolerance will be assessed to control for possible confounders ranging between 0 and 10 each.

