5.4 Safety Outcomes

Safety outcome variables will consist of rate of adverse events in general.

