11. STATISTICAL METHODS

A within-subject design is performed to achieve more Power than a between-subject design by partitioning between-subject variance out of the error variance. No carryover-effects (e.g. practice, fatigue) are expected.

A significance level of $p < 0.05$ (two-sided) will be considered as significant. As there is only one primary outcome measure, no Bonferroni correction will be applied.

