11.2 Determination of Sample Size

We are interested to detect cannabinol effects with at least medium effect sizes. The estimation of $N=34$ is based on a power analysis using dependent t-tests assuming to detect a medium effect size ($d_z = 0.5$) with a power of 80% at $\alpha = 0.05$ (software: G-power 3).

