11.4.4 Safety analysis

Safety analyses will be performed after data sampling completion analogue to the analyses of primary and secondary analyses.

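### The tiredness, headache and tolerance ratings taken after each product serve only as covariates, so no analysis explicitly estimates whether CBD changes them

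*Combined protocol and SAP*

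**What the plan says.** The safety objective in section 4.4 reads: "The study aims to assess tolerability of CBD in terms of incidence of side effects e.g. headache, gastrointestinal side effects etc". Section 3.7 names the main hazard: "Risks: sedative actions like somnolence and increase of sleep duration". The outcome set against these is narrower. Section 5.4 states: "Safety outcome variables will consist of rate of adverse events in general". For its analysis, section 11.4.4 says only: "Safety analyses will be performed after data sampling completion analogue to the analyses of primary and secondary analyses".

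Every participant also rates tiredness, headache and tolerance from 0 to 10, once per visit, after vaping and the n-back task, under both products. Section 5.3 describes these ratings so: "VAS of motivation, tiredness, headache and tolerance will be assessed to control for possible confounders ranging between 0 and 10 each". The study schedule lists them as confounding factors, and section 11.4 puts them among the possible confounders that enter the models one at a time as covariates. Section 5.3 introduces the mood and arousal VAS without the confounder wording, but section 11.4 places them in the same covariate list.

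**The concern.** The objective names headache and the risk section names sedation. The trial collects a graded rating of headache and of tiredness from the same person after CBD and after placebo, at the same point in the visit. The plan then uses those ratings only to adjust other outcomes.

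Two things are at stake. First, the report may not say whether CBD changed headache or tiredness, and tolerability would rest on AE counts from a small sample. Second, a difference in recall or n-back performance would be hard to interpret. A model that adjusts for tiredness does not report whether CBD caused tiredness, and it may remove the part of a CBD effect that acts through it.

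**Working it through.** **Inputs.** N = 34 completers, with drop-outs replaced (sections 7.4, 11.2, 11.3); two-sided 5% level (section 11); visit times from the study schedule; safety data analysed for everyone who received study medication (section 7.4). The documents give no expected AE rate and no standard deviation for any VAS.

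**1. The plan's own figure.** Section 11.2 says: "The estimation of $N=34$ is based on a power analysis using dependent t-tests", with dz = 0.5 and 80% power. For a two-sided paired t-test with 33 degrees of freedom, the noncentrality is 0.5 × √34 = 2.92 and the power is 80.8%. N = 34 is the smallest sample that reaches 80%, so the figure reproduces.

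**2. Role of the scales, place by place.**
- Study schedule: confounding factors.
- Section 5.3: confounder control.
- Section 5.4: not mentioned; AE rate only.
- Section 11.4: covariates, each entered separately. Where a covariate-by-condition interaction is examined, it asks whether the relation between the rating and recall differs by product. It does not ask whether the rating itself differs by product.
- Section 11.4.4: refers back to the efficacy methods and does not name the scales.

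**3. Timing.**
- Visit 1: AE log at 00:43, vaping 00:46 to 01:01, VAS at 01:16, end at 80 minutes.
- Visit 2: AE log at 00:08, vaping 00:11 to 00:26, VAS at 00:41, end at 45 minutes.

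The VAS falls 15 minutes after the end of vaping at both visits (01:16 − 01:01 and 00:41 − 00:26). The AE log falls 3 minutes before vaping at both visits. The visit 2 log can therefore pick up events after the first product, but no log is scheduled after the second. For the second product, the schedule leaves 45 − 26 = 19 minutes from the end of vaping to the end of the visit. AE recording after the first product can run through the 14 to 56 day interval as well. Randomised order balances this between CBD and placebo on average, but the counts come from unequal windows.

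**4. Precision of AE incidence.** With no events in n people, the 95% upper limit is 1 − 0.05^(1/n) one-sided and 1 − 0.025^(1/n) two-sided. For n = 34:
- one-sided: 1 − 0.05^(1/34) = 0.084, or 8.4%;
- two-sided: 1 − 0.025^(1/34) = 0.103, or 10.3%.

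Replaced drop-outs who were exposed would raise n and lower these limits.

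**5. Precision of a paired VAS estimate.** The 95% half-width is t(0.975, 33) × SD/√34 = 2.035 × SD/5.831 = 0.349 × SD, where SD is that of the within-person difference. For assumed SDs of 1, 2 and 3 points it is 0.35, 0.70 and 1.05 points on the 0 to 10 scale.

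**6. Tiredness as covariate.** Let a be the effect of CBD on tiredness, b the effect of tiredness on recall, and c the effect of CBD on recall by other routes. In a simple linear model the total effect is c + a × b. A model adjusted for post-vaping tiredness targets c and reports b. No planned model explicitly reports a.

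**The case against.** Much of the opposing case stands.

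- A reader might infer that the VAS are the only systematic tolerability enquiry. They are not. Section 9.3 ends each test day with an interview on well-being, and sections 9.2.4.1 and 10.4.2 require AEs to be recorded with details such as intensity or severity and causality. What can be said is that the interview has no described scale or checklist, and that the VAS are the only quantified side-effect ratings at a fixed time after each product.
- Section 4.4 states tolerability as an incidence, and section 5.4 answers with an incidence. A mean VAS difference cannot replace that. No scale covers the gastrointestinal effects that section 4.4 names, and there is no rating before vaping.
- Section 11.4 plans mixed models for secondary variables of interest, a term it does not define, and section 5.3 is headed as other outcomes. The VAS might be meant. But the same section 11.4 names them as confounders, so a treatment comparison is possible and not stated.
- A reader might set the planned 80% power at dz = 0.5 against the difficulty of showing an AE difference in 34 pairs. The documents do not support that contrast. The effect size was chosen for the sample size calculation under a hypothesis about episodic memory, nothing shows that it applies to headache or tiredness, and no test of AEs is specified.
- A reader might infer that the scale end points run in opposing directions. Section 5.3 gives verbal end points for mood and arousal only; for the other scales it gives just the numeric range.
- The study is minimal-risk basic research with a single low exposure, and the memory conclusion does not depend on a safety table. This limits the weight of the point. It does not justify leaving collected data without a stated comparison.

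**Conclusion.** The concern holds in a limited form. The tiredness, headache and tolerance ratings are taken from everyone at the same point after each product, but every place that states their role makes them confounders or covariates. No analysis explicitly estimates whether CBD changes headache or tiredness. The safety outcome is the AE rate alone. With no events in 34 people it would leave true rates of up to 8.4% (one-sided) or 10.3% (two-sided) compatible with the data. These are limits at the planned minimum denominator and become smaller if more people are exposed. That AE counts will be low is an assumption, since the documents give no rate.

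This is an improvement available at almost no cost. It does not undermine the primary analysis or the sample size. The VAS precision figures rest on assumed SDs of 1 to 3 points.

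**What to change.** - **Sections 5.4 and 11.4.4:** name the post-vaping tiredness, headache and tolerance VAS, and the arousal VAS because it bears on sedation, as descriptive tolerability outcomes. For each, report the within-person CBD minus placebo difference with a 95% confidence interval, beside AE incidence by condition. State that the ratings supplement AE incidence, do not cover gastrointestinal effects and have no baseline before vaping.
- **Section 5.3:** remove confounder control as the sole purpose of these scales.
- **Section 11.4:** label memory models adjusted for post-vaping VAS as sensitivity analyses, with the model that omits them as the main estimate of the CBD effect.

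The cost is a few descriptive paired estimates and some rewording. No visit, assessment or participant is added, and N stays at 34.
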